9.6. Concomitant Medications

9.6.1 Permitted Concomitant Therapy

- Standard therapies for concurrent medical conditions
- Treatment with non-conventional therapies (for example herbs or acupuncture), and vitamin/mineral supplements is acceptable provided that they do not interfere with the study endpoints, in the opinion of the Investigator. St John's Wort is not permitted.
- Bisphosphonates
- Close monitoring is recommended according to standard of care. If either of these values is above the therapeutic range, the doses should be modified and the assessments should be repeated weekly until it is stable.
- Antiemetics: Prophylactic anti-emetics may be administered according to standard practice. The routine use of standard antiemetics, including steroids, 5-HT3 blockers, such as granisetron, ondansetron, or an equivalent agent, is allowed as needed.
- Palliative and supportive care for the other disease-related symptoms and for toxicity associated with treatment will be offered to all patients in this trial.
- Patients may receive palliative and supportive care for any underlying disease
- Palliative irradiation shall be permitted provided that:
 - In the opinion of the investigator, the patient does not have progression of disease.
 - The radiation field does not encompass a target lesion
 - The radiation field does not encompass a lung field (to reduce the risk for pneumonitis).
- Low-dose aspirin (maximum 100 mg/day) and low-dose heparin are permitted.
- Patients taking narrow therapeutic index medications should be monitored proactively, if these medications cannot be avoided. These medications may include quinidine, cyclosporine, and digoxin
- Short term systemic corticosteroids will be allowed for the management of acute conditions
- Use of neutrophil growth factors (filgrastim and pegfilgrastim) is not permitted in the dose escalation phase during cycle 1 unless a DLT has already been determined. Neutrophil growth factor support is allowed in the dose expansion portion of the study to treat neutropenia but not prophylactically.

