During phase II, strong inducers of CYP3A such as enzyme-inducing anti-epileptics (carbamazepine, phenytoin, etc), rifampin, and St. John's Wort etc, should be avoided. Co-administration of ibrutinib with strong CYP3A inducers, rifampin, in healthy subjects decrease ibrutinib plasma concentrations by approximately 10-fold. Consider alternative agents with less CYP3A induction. If strong CYP3A inducers cannot be avoided, consider holding ibrutinib and copanlisib while on CYP3A inducer if it will be used short-term. Re-initiate ibrutinib and copanlisib after 5 to 6 half-life washout period of the CYP3A inducer. Additionally, corticosteroid doses more than 4mg oral daily of dexamethasone-equivalent (>26mg prednisone) may induce CYP3A enzyme, so need to be discussed with investigators.

A list of common, moderate to strong, CYP3A inhibitors or inducers is provided in the appendices; a comprehensive list of inhibitors, inducers, and substrates may be found at <http://medicine.iupui.edu/clinpharm/ddis/main-table/>. This website is continually revised and should be checked frequently for updates (Appendix 1).

Sensitive substrates of CYP3A should be used with caution. A comprehensive list of sensitive substrates of CYP3A could be found on FDA website: <https://www.fda.gov/drugs/developmentapprovalprocess/developmentresources/druginteractionslabeling/ucm093664.htm#table3-1>.

Concomitant Use of Antiplatelet Agents and Anticoagulants

Ibrutinib may increase the risk of hemorrhage in patients receiving antiplatelet or anticoagulant therapies. The mechanism for this bleeding is not well understood.

Warfarin or vitamin K antagonists should not be administered concomitantly with ibrutinib or copanlisib. Supplements such as fish oil and vitamin E preparations should be avoided. Use ibrutinib with caution in subjects requiring other anticoagulants or medications that inhibit platelet function.

Subjects receiving antiplatelet agents in conjunction with ibrutinib should be observed closely for any signs of bleeding or bruising and ibrutinib should be withheld in the event of any bleeding events.

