Subjects requiring the initiation of anticoagulation therapy (other than warfarin or a vitamin K antagonist, which should be avoided) during the course of the study should have treatment with ibrutinib held, the PI should be contacted, and ibrutinib should not be restarted until the subject is clinically stable. Subjects should be observed closely for signs and symptoms of bleeding.

Subjects were excluded from participation in ibrutinib Phase 2 and 3 studies if they required warfarin or other vitamin K antagonists. Therefore, ibrutinib should not be administered concomitantly with warfarin or other vitamin K antagonists. Ibrutinib should be used with caution in patients requiring other anticoagulants or medications that inhibit platelet function. Patients receiving antiplatelet agents in conjunction with ibrutinib should be observed closely for any signs of bleeding or bruising and ibrutinib should be withheld in the event of any bleeding events. Supplements such as fish oil and vitamin E preparations should be avoided. Patients with congenital bleeding diathesis have not been studied.

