Each patient is allowed a maximum of two dose reduction of each study drug. Dose reduction of copanlisib or ibrutinib indicates treatment at the next lower dose of copanlisib or ibrutinib based on Table 9-6. If after treatment interruption, resolution of toxicity, and treatment resumption at same dose, the subject presents with the same toxicity at the same severity, then the next treatment re-

initiation must resume at the next lower dose level irrespective of duration. A patient must discontinue therapy if after therapy is resumed at a lower dose, the same toxicity recurs with the same or worse severity. Copanlisib and ibrutinib dose modification guidelines for specific toxicities are outlined in Table 9-7.

Table 9-6. Intrapatient dose reduction*

Drug	Maximum Dose Levels	Reduction Dose Level 1	Reduction Dose Level 2
Copanlisib	60 mg	45 mg	30 mg
Ibrutinib	560 mg daily	420 mg daily	280 mg daily

*Dose reduction starts from the treating dose.

Dose escalation is allowed after the DLT period for ibrutinib to the FDA approved dose levels of 560 mg. However, patients will only be allowed to escalate to this dose once the DLT evaluation period for Dose Level 1 has passed and the dose will not exceed what has been deemed the MTD in other patients. There will be no intrapatient dose escalation of copanlisib. Once a dose reduction for copanlisib of a patient has occurred, the dose level may not be re-escalated during subsequent treatment cycles.

The sections below describe dose reduction steps for patients enrolled in the expansion phase of the study. For patients in the dose expansion phase, the dose must be held per these guidelines and these dose reduction steps can be followed after cycle 1 and per discussion with the PI. Inability to meet treatment criteria will result in holding the dose. If patients have been dose reduced to dose level -1 and continue to meet dose modification criteria to reduce the dose, they will be removed from study treatment.

Table 9-7. Dose modification guidelines

Toxicity Category	Severity (CTCAE 5.0 Grade)	Dose Modifications for ibrutinib	Dose Modifications for copanlisib
HEMATOLOGIC			

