	Grade 4 (PLT < 25 x 10 ⁹ /L)	Delay ibrutinib dose until resolves to ≤ Grade 1, then reduce 1 dose level	Dose reduction by 1 dose level lower at the investigator's discretion. If more dose reductions are required than allowed per protocol, discontinue copanlisib permanently. The lowest dose level is 30 mg.
Dose modify/hold ibrutinib because of association with hemorrhagic event. May dose modify/hold copanlisib as clinically indicated			
Bleeding	Grade 1 (mild symptoms; no intervention indicated)	Maintain ibrutinib dose	Maintain copanlisib dose
	Grade 2 bleeding (medical intervention indicated/cauterization)	Omit ibrutinib dose until resolves to ≤ Grade 1, then reduce 1 dose level ibrutinib	Delay copanlisib infusion Dose reduction by 1 dose level lower at the investigator's discretion. If more dose reductions are required than allowed per protocol, discontinue copanlisib permanently. The lowest dose level is 30 mg.
	Grade ≥ 3 hemorrhage or hemorrhage resulting in intraocular bleeding causing loss of vision, transfusion of ≥ 2 units PRBCs, and any intracranial hemorrhage	Discontinue ibrutinib	Discontinue copanlisib
RENAL	May dose modify/hold either ibrutinib, copanlisib or both as clinically indicated		
Creatinine elevation	Grade 1 (Cr < 2 x ULN)	Maintain ibrutinib dose	Maintain copanlisib dose
	Grade 2 (Cr 2-3x ULN)	Delay ibrutinib dose until resolves to ≤ Grade 1, then: If resolved ≤ 7 days, then maintain dose level If resolved > 7 days, then reduce 1 dose level	Maintain copanlisib dose
	Grade ≥ 3 (Cr > 3-6 x ULN)	Discontinue ibrutinib	First occurrence: Delay copanlisib infusion until resolves to ≤ Grade 2, no change to next dose Second and Third occurrence: Delay copanlisib infusion until resolves to ≤ Grade 2, decrease by one dose level Fourth occurrence: Discontinue copanlisib *Any grade 4 occurrence: discontinue copanlisib
PULMONARY	Dose modify/hold copanlisib because of association with pneumonitis. May dose modify/hold ibrutinib as clinically indicated		
Pneumonitis	Grade 1		Dose delay copanlisib while treating infection. Resume at same dose once infection resolves
	Grade 2		Dose delay until resolves to ≤ Grade 1. Decrease by one dose level. Second occurrence: Discontinue therapy If no symptom recovery ≤ Grade 1 within 28 days CT scan with lung windows. Consider pulmonary function testing includes: spirometry, DLCO, and room air O ₂ saturation at rest. Repeat at least every 8 weeks (+/- 1)

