11.6. Ibrutinib adverse events of special interest

Hemorrhagic Adverse Events

Fatal bleeding events have occurred in patients treated with ibrutinib. Grade 3 or higher bleeding events (subdural hematoma, gastrointestinal bleeding, hematuria and post procedural hemorrhage) have occurred in up to 6% of patients. Bleeding events of any grade, including bruising and petechiae, occurred in approximately half of patients treated with ibrutinib. The mechanism for the bleeding events is not well understood. Ibrutinib may increase the risk of hemorrhage in patients receiving antiplatelet or anticoagulant therapies.

Subjects in the current study will be monitored closely for hemorrhagic adverse events. Ibrutinib should be held at least 3 to 7 days pre and post-surgery depending upon the type of surgery and the risk of bleeding (please refer to Section 9.7 for further details).

Infection

Fatal and non-fatal infections have occurred with ibrutinib therapy. Grade 3 or greater infections occurred in 14% to 29% of patients. Cases of progressive multifocal leukoencephalopathy (PML) have occurred in patients treated with ibrutinib. Monitor patients for fever and infections and evaluate promptly.

Cytopenias

Treatment-emergent Grade 3 or 4 cytopenias including neutropenia (range, 19 to 29%), thrombocytopenia (range, 5 to 17%), and anemia (range, 0 to 9%) occurred in patients treated with ibrutinib. Monitor complete blood counts monthly.

Atrial Fibrillation

Atrial fibrillation and atrial flutter (range, 6 to 9%) have occurred in patients treated with ibrutinib, particularly in patients with cardiac risk factors, acute infections, and a previous history of atrial fibrillation. Periodically monitor patients clinically for atrial fibrillation. Patients who develop arrhythmic symptoms (e.g., palpitations, lightheadedness) or new onset dyspnea should have an ECG performed. If atrial fibrillation persists, consider the risks and benefits of ibrutinib treatment and dose modification based on recommendations in Section 9.

Hypertension

Hypertension (range, 6 to 17%) has occurred in patients treated with ibrutinib with a median time to onset of 4.6 months (range, 0.03 to 22 months). Monitor patients for new onset hypertension or hypertension that is not adequately controlled after starting ibrutinib. Adjust existing anti-hypertensive medications and/or initiate anti-hypertensive treatment as appropriate.

Secondary Primary Malignancies

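### For patients on an antiplatelet agent, Section 9.6.3 withholds ibrutinib for any bleeding event while Table 9-7 maintains it at Grade 1, and nothing says which applies

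*Combined protocol and SAP*

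**What the plan says.** Four parts of the combined protocol and SAP bear on this.

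- **Section 9.6.3, on antiplatelet agents and anticoagulants.** Patients taking an antiplatelet agent with ibrutinib are to be watched closely, and "ibrutinib should be withheld in the event of any bleeding events". The instruction appears twice, the second time after "Patients receiving antiplatelet agents in conjunction with ibrutinib should be observed closely for any signs of bleeding or bruising". Neither statement names a grade or says when ibrutinib may resume.
- **Section 9.7, Table 9-7, bleeding row.** The table is introduced by "Copanlisib and ibrutinib dose modification guidelines for specific toxicities are outlined in Table 9-7". For the lowest severity, "Grade 1 (mild symptoms; no intervention indicated", the ibrutinib action is "Maintain ibrutinib dose". For Grade 2 it is "Omit ibrutinib dose until resolves to ≤ Grade 1, then reduce 1 dose level ibrutinib". For Grade 3 or higher, and for the listed major hemorrhages, ibrutinib is discontinued. The row does not mention antiplatelet use.
- **Section 9.6.1.** "Low-dose aspirin (maximum 100 mg/day) and low-dose heparin are permitted".
- **Section 11.6.** Hemorrhage is an adverse event of special interest for ibrutinib, with fatal cases on record. "Bleeding events of any grade, including bruising and petechiae, occurred in approximately half of patients treated with ibrutinib". Grade 3 or higher bleeding is put at up to 6%.

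**The concern.** A patient on permitted aspirin who has a Grade 1 bleed meets both rules. One says to stop ibrutinib and the other says to carry on at the same dose. Table 9-7 is where a clinician would look when dosing, and nothing in it shows that another section treats antiplatelet users differently.

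The first thing at stake is safety: a hold that the protocol states twice can be missed by someone following the protocol's own dosing table. The second is consistency of exposure: two patients with the same event could be handled differently according to which section their clinician read. The trial is run at a single institution, so the variation would be between treating clinicians, not between sites.

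**Working it through.** This is a comparison of texts. The plan states no figure on this point that could be reproduced.

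**Step 1. The two rules by grade, for a patient on an antiplatelet agent**

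| Bleeding grade | Section 9.6.3 | Table 9-7, ibrutinib column | Do both stop ibrutinib? |
|---|---|---|---|
| 1 | Withhold | Maintain | No |
| 2 | Withhold | Omit until Grade 1 or lower, then one level down | Yes |
| 3 or higher, or listed major hemorrhage | Withhold | Discontinue | Yes, and the table goes further |

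The disagreement lies in the Grade 1 line alone.

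**Step 2. Can one patient fall under both?** Yes. Section 9.6.1 permits low-dose aspirin, and Table 9-7 applies to bleeding whatever the concomitant medication.

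**Step 3. Does any text settle precedence?** None was found.

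- The header of the bleeding row ties ibrutinib holds to hemorrhagic events in general terms, but the Grade 1 cell beneath it still maintains the dose.
- The closing notes to Table 9-7 tell the investigator to hold and reduce a drug associated with a toxicity. They mention neither antiplatelet agents nor Grade 1 bleeding.
- The hemorrhage guidance in Section 9.8 and the text of Section 11.6 repeat that antiplatelet therapy may raise the bleeding risk, but give no rule for this case.

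**Step 4. Where does it apply?** Section 9.7 introduces the dose-reduction steps as being for the expansion phase, and its statement that doses must be held under these guidelines is limited to that phase. The conflict therefore matters mainly in phase II.

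**Step 5. How many patients?** The only rates are those in Section 11.6: about 50% with bleeding of any grade and up to 6% with Grade 3 or higher. If both figures describe the same patients:

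- 50% − 6% = 44%, so at least about 44% of patients had bleeding no worse than Grade 2.
- 44 / 50 = 88% of those who bled.

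Low-grade bleeding is thus the large majority, but Grade 1 is not separated from Grade 2. The number in conflict would be N × a × g, where a is the share of patients on an antiplatelet agent and g is the share of those with a Grade 1 bleed. The documents give neither a nor g, so no count follows.

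**The case against.** The strongest reply is that a specific rule governs a general one. Section 9.6.3 addresses a defined subgroup and Table 9-7 addresses everyone, so the subgroup caution can be read as an addition to the table. That is a reasonable reading and may be what was intended. The protocol does not say so, however, and a clinician who opens only the table has no way of knowing. The reply explains the gap without closing it.

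A second reply is that bruising was never meant to trigger the hold. The sentence in Section 9.6.3 attaches close observation to signs of bleeding or bruising, and withholding to bleeding events. Section 11.5 lists bruising and petechiae apart from hemorrhage. On the other side, Section 11.6 counts both as bleeding events, although it is summarizing past experience and not defining a dosing trigger. The objection stands this far: the bruise is an uncertain example. It does not remove the conflict, because another Grade 1 bleed, such as a mild nosebleed (epistaxis is listed in Section 11.5), can still meet both rules.

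A third reply is that Section 9.7 lets either drug be interrupted for any reason, for up to 7 days before the end of cycle 1 and up to 28 days afterwards. A hold under Section 9.6.3 is therefore an allowed interruption. This is correct, and Section 9.6.3 says *should*, which leaves some discretion. But permission to interrupt does not tell the clinician whether to do so, and a time limit is not a restart condition. The neighboring paragraph on starting anticoagulation does give one, namely clinical stability.

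**Conclusion.** The inconsistency is real but narrow: Grade 1 bleeding in a patient on an antiplatelet agent. It should be corrected because it concerns a safety instruction for an adverse event of special interest and is cheap to remove. It does not undermine the design. The conclusion rests on low-dose aspirin counting as an antiplatelet agent under Section 9.6.3, and on the absence of any precedence text.

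A reader might infer more, but the documents do not support it:

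- **An indefinite hold.** Section 9.6.3 gives no restart condition, but the general limits of 7 and 28 days in Section 9.7 still apply.
- **A change in DLT counts or in a 3+3 decision.** The DLT item in Section 9.2 on delays above 7 days refers to dose modifications under Table 9-6. A hold for concomitant medication is not shown to be one. The mandatory holds of Section 9.7 are also scoped to expansion, while the 3+3 decision belongs to escalation.
- **An effect on event-free survival.** Discontinuation after 28 days is for unacceptable toxicity that has not resolved, with an exception for patients who are benefiting. The rule on recurrent toxicity could lead from a hold to a reduction and then to discontinuation, but only after repeated bleeds, for which no rate is given.
- **A patient count.** Assuming 10–40% antiplatelet use among 33 patients gives 3.3–13.2, and halving for any-grade bleeding gives 1.7–6.6. The first factor is invented for the purpose, and the second covers all grades although only Grade 1 conflicts.
- **That these are the commonest bleeding events.** Low grades dominate, but no Grade 1 rate is stated.

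**What to change.** Reconcile Section 9.6.3 with the Grade 1 bleeding row of Table 9-7 so that both give the same instruction for patients on antiplatelet agents. This can be done with a footnote or added row in the table, or by changing the sentence in Section 9.6.3 in both places where it appears. In addition:

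- cross-reference the two places;
- state whether bruising and petechiae count as bleeding events for this rule;
- if a hold is kept, state how it ends.

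Which instruction applies is a clinical decision for the sponsor.

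The cost is a footnote or a changed sentence in an amendment. No procedure, visit or data item is added, and the sample size and analyses are unaffected.

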9.7. Dose Continuation, Modification and Interruption

Subjects will be evaluated for AEs at each visit with the NCI CTCAE v5.0 used as a guide for the grading of severity. Prior to completion of cycle 1 in both dose escalation or dose expansion phase, treatment with either ibrutinib, copanlisib or both may be interrupted for \leq 7 days for any reason and then resumed at the same dose. If patients take less than 2 infusions of copanlisib or less than 14 days of ibrutinib during the intended dose of cycle 1, they will be excluded from the DLT analysis and replaced. However if a patient takes less than 14 days of the intended dose of cycle 1 due to a DLT, they will be included in the DLT analysis and not replaced. After completion of cycle 1, study drugs (either ibrutinib, copanlisib) may be interrupted for \leq 28 days for any reason and then resumed at same or reduced dose. The investigator may remove any patient from study for any toxicity if the investigator believes it is in the best interest of the patient to discontinue study treatment.

Intrapatient dose reduction will not be allowed during cycle 1 unless a DLT has occurred and been counted. This is in order to accurately determine the safe and tolerable dose of copanlisib when used in combination with ibrutinib. Dose reductions may be made to ibrutinib and/or copanlisib during cycles 2 and beyond. If a toxicity can be ascribed to a specific study drug, then that drug may be dose modified while the non-offending drug may be maintained. Whether to dose modify ibrutinib or copanlisib is at the discretion of the treating physician.

If the patient experiences unacceptable toxicity that fails to resolve after a maximum dose delay of 28 consecutive days, then the patient should be discontinued from the study treatments. In cases of treatment delays from reactivation of CMV, treatment delays can be extended for up to 2 months. In exceptional situations, if the patient is clearly benefiting from the study treatment (i.e. stable disease or better) and in the opinion of the investigator no safety concerns are present, the patient may remain on the study treatment. Patients who discontinue from study for a study related adverse event or an abnormal laboratory value must be followed as described in Section 10.

Each patient is allowed a maximum of two dose reduction of each study drug. Dose reduction of copanlisib or ibrutinib indicates treatment at the next lower dose of copanlisib or ibrutinib based on Table 9-6. If after treatment interruption, resolution of toxicity, and treatment resumption at same dose, the subject presents with the same toxicity at the same severity, then the next treatment re-

initiation must resume at the next lower dose level irrespective of duration. A patient must discontinue therapy if after therapy is resumed at a lower dose, the same toxicity recurs with the same or worse severity. Copanlisib and ibrutinib dose modification guidelines for specific toxicities are outlined in Table 9-7.

Table 9-6. Intrapatient dose reduction*

Drug	Maximum Dose Levels	Reduction Dose Level 1	Reduction Dose Level 2
Copanlisib	60 mg	45 mg	30 mg
Ibrutinib	560 mg daily	420 mg daily	280 mg daily

*Dose reduction starts from the treating dose.

Dose escalation is allowed after the DLT period for ibrutinib to the FDA approved dose levels of 560 mg. However, patients will only be allowed to escalate to this dose once the DLT evaluation period for Dose Level 1 has passed and the dose will not exceed what has been deemed the MTD in other patients. There will be no intrapatient dose escalation of copanlisib. Once a dose reduction for copanlisib of a patient has occurred, the dose level may not be re-escalated during subsequent treatment cycles.

The sections below describe dose reduction steps for patients enrolled in the expansion phase of the study. For patients in the dose expansion phase, the dose must be held per these guidelines and these dose reduction steps can be followed after cycle 1 and per discussion with the PI. Inability to meet treatment criteria will result in holding the dose. If patients have been dose reduced to dose level -1 and continue to meet dose modification criteria to reduce the dose, they will be removed from study treatment.

Table 9-7. Dose modification guidelines

Toxicity Category	Severity (CTCAE 5.0 Grade)	Dose Modifications for ibrutinib	Dose Modifications for copanlisib
HEMATOLOGIC			
Anemia	Grade ≥ 3 (Hgb <8 g/dL)	Investigator discretion for ibrutinib dosing	
Delay copanlisib infusion until Hgb resolves to \leq grade 3
 
Dose reduction by 1 dose level lower at the investigator's discretion. If more dose reductions are required than allowed per protocol, discontinue copanlisib permanently. The lowest dose level is 30 mg.

May dose modify/hold either ibrutinib, copanlisib or both as clinically indicated			
Neutropenia	Grade 1 (ANC < LLN - $1.5 \times 10^9/L$) Grade 2 (ANC < $1.5 - 1.0 \times 10^9/L$)	Maintain ibrutinib dose	Maintain copanlisib dose
	Grade ≥ 3 (ANC < $1.0 \times 10^9/L$)	
Delay ibrutinib dose until resolves to \leq Grade 1, then: If resolved \leq 7 days, then maintain dose level If resolved $>$ 7 days, then reduce 1 dose level
 
Growth factor support is allowed after cycle 1.
	
Delay copanlisib infusion until ANC resolves to $<$ grade 3
 
Dose reduction by 1 dose level lower at the investigator's discretion. If more dose reductions are required than allowed per protocol, discontinue copanlisib permanently. The lowest dose level is 30 mg.
 
Growth factor support is allowed after cycle 1.

	Febrile neutropenia ($ANC < 1.0 \times 10^9/L$, with a single temperature of $\geq 38.3^\circ C$ or a sustained temperature of $\geq 38^\circ C$ for more than one hour)	
Delay ibrutinib dose until resolves to \leq Grade 1, then reduce 1 dose level
 
Growth factor support is allowed after cycle 1.
	
Delay copanlisib until febrile neutropenia resolves
 
Dose reduction by 1 dose level lower at the investigator's discretion. If more dose reductions are required than allowed per protocol, discontinue copanlisib permanently. The lowest dose level is 30 mg.
 
Growth factor support is allowed after cycle 1.

May dose modify/hold either ibrutinib, copanlisib or both as clinically indicated			
Thrombocytopenia	Grade 1 (PLT < LLN - $75 \times 10^9/L$) Grade 2 (PLT < $75 - 50 \times 10^9/L$)	Maintain ibrutinib dose	Maintain copanlisib dose
	Grade 3 (PLT < $50-25 \times 10^9/L$)	
Delay ibrutinib dose until resolves to \leq Grade 1, then: If resolved \leq 7 days, then maintain dose level If resolved $>$ 7 days, then reduce 1 dose level
	Delay copanlisib infusion until platelet resolves to $>75k$

	Grade 4 (PLT < 25 x 10 ⁹ /L)	Delay ibrutinib dose until resolves to ≤ Grade 1, then reduce 1 dose level	Dose reduction by 1 dose level lower at the investigator's discretion. If more dose reductions are required than allowed per protocol, discontinue copanlisib permanently. The lowest dose level is 30 mg.
Dose modify/hold ibrutinib because of association with hemorrhagic event. May dose modify/hold copanlisib as clinically indicated			
Bleeding	Grade 1 (mild symptoms; no intervention indicated)	Maintain ibrutinib dose	Maintain copanlisib dose
	Grade 2 bleeding (medical intervention indicated/cauterization)	Omit ibrutinib dose until resolves to ≤ Grade 1, then reduce 1 dose level ibrutinib	Delay copanlisib infusion Dose reduction by 1 dose level lower at the investigator's discretion. If more dose reductions are required than allowed per protocol, discontinue copanlisib permanently. The lowest dose level is 30 mg.
	Grade ≥ 3 hemorrhage or hemorrhage resulting in intraocular bleeding causing loss of vision, transfusion of ≥ 2 units PRBCs, and any intracranial hemorrhage	Discontinue ibrutinib	Discontinue copanlisib
RENAL	May dose modify/hold either ibrutinib, copanlisib or both as clinically indicated		
Creatinine elevation	Grade 1 (Cr < 2 x ULN)	Maintain ibrutinib dose	Maintain copanlisib dose
	Grade 2 (Cr 2-3x ULN)	Delay ibrutinib dose until resolves to ≤ Grade 1, then: If resolved ≤ 7 days, then maintain dose level If resolved > 7 days, then reduce 1 dose level	Maintain copanlisib dose
	Grade ≥ 3 (Cr > 3-6 x ULN)	Discontinue ibrutinib	First occurrence: Delay copanlisib infusion until resolves to ≤ Grade 2, no change to next dose Second and Third occurrence: Delay copanlisib infusion until resolves to ≤ Grade 2, decrease by one dose level Fourth occurrence: Discontinue copanlisib *Any grade 4 occurrence: discontinue copanlisib
PULMONARY	Dose modify/hold copanlisib because of association with pneumonitis. May dose modify/hold ibrutinib as clinically indicated		
Pneumonitis	Grade 1		Dose delay copanlisib while treating infection. Resume at same dose once infection resolves
	Grade 2		Dose delay until resolves to ≤ Grade 1. Decrease by one dose level. Second occurrence: Discontinue therapy If no symptom recovery ≤ Grade 1 within 28 days CT scan with lung windows. Consider pulmonary function testing includes: spirometry, DLCO, and room air O ₂ saturation at rest. Repeat at least every 8 weeks (+/- 1)

			week), (or as per local practice) until return to within normal limits. Consider a bronchoscopy with biopsy and / or BAL.
	Grade \geq 3		Discontinue copanlisib
GASTROINTESTINAL	May dose modify/hold either ibrutinib, copanlisib or both as clinically indicated		
(*for patients with Gilbert Syndrome these dose modifications apply to changes in direct bilirubin only, Bilirubin will be fractionated if elevated)	Grade 1 ($>$ ULN - 1.5 \times ULN)	Maintain ibrutinib dose per investigator discretion	Maintain copanlisib dose level with LFTs* monitored as per protocol
	Grade 2 ($>$ 1.5 - 3.0 \times ULN) with ALT or AST \leq 3.0 \times ULN	Dose adjustments of ibrutinib per investigator discretion	Omit dose until resolves to \leq Grade 1, then: If resolved \leq 7 days, then maintain dose level If resolved $>$ 7 days, then reduce 1 dose level
	Grade 3 ($>$ 3.0 - 10.0 \times ULN) with ALT or AST \leq 3.0 \times ULN		Omit dose until resolves to \leq Grade 1, then: If resolved \leq 7 days, then maintain dose level If resolved $>$ 7 days, then discontinue
	Grade 4 ($>$ 10.0 \times ULN)	Discontinue ibrutinib	Discontinue copanlisib
Note: confounding factors and/or alternative causes for increased transaminases like concomitant medications, infection, hepato-biliary disorder, obstruction, liver metastasis, etc. should be excluded before dose interruption/reduction	Grade 1 ($>$ ULN - 3.0 \times ULN)	Maintain ibrutinib dose per investigator discretion	Maintain dose level with LFTs monitored as per protocol
	Grade 2 ($>$ 3.0 - 5.0 \times ULN) without total bilirubin elevation to $>$ 2.0 \times ULN	Dose adjustments of ibrutinib per investigator discretion	Maintain dose or reduce 1 dose level of copanlisib.
	Grade 3 ($>$ 5.0 - 20.0 \times ULN) without total bilirubin elevation to $>$ 2.0 \times ULN		Omit dose until resolves to \leq Grade 1, then reduce 1 dose level. If no recovery in \leq 28 days discontinue copanlisib, patient off study
	Grade 4 ($>$ 20.0 \times ULN) without bilirubin elevation to $>$ 2.0 \times ULN	Discontinue ibrutinib	Discontinue copanlisib
AST or ALT Elevation and concurrent bilirubin elevation	AST or ALT $>$ 3.0 \times ULN and total bilirubin $>$ 2.0 \times ULN	Discontinue ibrutinib *** All patients with ALT or AST $>$ 3.0 \times ULN and total bilirubin $>$ 2.0 \times ULN in the absence of cholestasis ULN must immediately be withdrawn from copanlisib and every attempt should be made to carry out the liver event follow-up assessments	Discontinue copanlisib
Pancreatitis	Grade 2 (enzyme elevation or radiographic findings)	Dose adjustments of ibrutinib per investigator discretion	Dose adjustments of copanlisib per investigator discretion
	Grade 3 (medical intervention indicated)	Discontinue ibrutinib	Discontinue copanlisib

*** Hepatic toxicity monitoring (*for patients with Gilbert Syndrome: total and direct bilirubin must be monitored, intensified monitoring applies to changes in direct bilirubin only; the monitoring includes the following LFTs: albumin, ALT, AST, total bilirubin (fractionated if total bilirubin $> 2.0 \times \text{ULN}$), alkaline phosphatase (fractionated if alkaline phosphatase is grade 2 or higher) and GGT):

In case of any occurrence of ALT/AST, or bilirubin* increase \geq grade 2 the liver function tests must be monitored weekly or more frequently if clinically indicated until resolved to \leq grade 1

In case of any occurrence of ALT/AST, or bilirubin* increase \geq grade 3 the liver function tests must be monitored weekly or more frequently if clinically indicated until resolved to \leq grade 1; hereafter the monitoring should be continued every other week or more frequently if clinically indicated until the end of treatment with study medication

Patients who discontinued study treatment should be monitored weekly, including LFTs* or more frequently if clinically indicated until resolved to \leq grade 1 or stabilization (no CTCAE grade change over 4 weeks).

ENDOCRINE

Dose modify/hold copanlisib because of association with hyperglycemia. May dose modify/hold ibrutinib as clinically indicated			
Hyperglycemia	Level 1: Fasting glucose $> 125 - 160 \text{ mg/dL}$		Maintain copanlisib dose level
	Level 2: Fasting glucose $> 160 - 250 \text{ mg/dL}$	Maintain ibrutinib dose per investigator discretion	
Maintain copanlisib dose level.
 
 If signs or symptoms of hyperglycemia (for example, mental status changes, excessive thirst, polyuria), manage as for Level 3 hyperglycemia (see below) If asymptomatic, maintain dose and re-check FPG within 24 hours. If level worsens or improves then follow specific level recommendations. If FPG remains at Level 2: 
 Maintain dose level and monitor FPG at least weekly until FPG resolves to \leq Level 1 Initiate or intensify medication with appropriate anti-diabetic treatment such as metformin; consider adding a second oral agent if not improvement after several days. Instruct patient to follow dietary guidelines according to local and/or institutional standards for management of diabetes mellitus (such as those provided by the American Diabetes Association) during the study If FPG does not resolve to \leq Level 1 within 14 days after institution of appropriate anti-diabetic treatment reduce copanlisib by 1 dose level Consider referral to endocrinologist for diabetic management
	Level 3: $> 250 - 500 \text{ mg/dL} (> 13.9 - 27.8 \text{ mmol/L})$		
Immediately omit copanlisib, initiate or intensify medication with appropriate anti-diabetic treatment, re-check FPG within 24 hours. If level worsens or improves then follow specific level recommendations.
 
If FPG remains at Level 3:

			
• Administer intravenous hydration and intervention for electrolyte/ ketoacidosis/hyperosmolar disturbances as clinically appropriate• Continue to omit copanlisib• Monitor FPG at least twice weekly until FPG resolves to \leq Level 1 
If FPG resolves to $<$ Level 1 in 7 days or less, then re-start copanlisib and reduce by 1 dose dose level
 
If FPG remains greater than Level 1 severity for more than 7 days, then discontinue patient from copanlisib
 
• Initiate or continue anti-diabetic treatment as appropriate
◦ instruct patient to follow dietary guidelines according to local and/or institutional standards for management of diabetes mellitus (such as those provided by the American Diabetes Association) during the study◦ consider use of oral anti-hyperglycemic therapy such as metformin• Consider referral to endocrinologist for diabetic management
	
Level 4: > 500 mg/dL (≥ 27.8 mmol/L)
	
Dose adjustments of ibrutinib per investigator discretion
	
Immediately omit copanlisib, initiate or intensify medication with appropriate anti-diabetic treatment, re-check within 24 hours. If level improves then follow specific level recommendations.
 
If FPG is confirmed at Level 4:
 
• Administer intravenous hydration and intervention for electrolyte/ ketoacidosis/hyperosmolar disturbances as clinically appropriate• Discontinue patient from study• Instruct patient to follow dietary guidelines according to local and/or institutional standards for management of diabetes mellitus (such as those provided by the American Diabetes Association) during the study• Consider use of oral anti-hyperglycemic therapy such as metformin• Consider referral to endocrinologist for diabetic management 
For non-fasting plasma glucose >500 mg/dL (> 27.8 mmol/L) accompanied by signs/symptoms of hyperglycemia (for example, mental status changes, excessive thirst, polyuria), or presence of blood or urine

			ketones, discontinue copanlisib and following guidance for management of Level 4 fasting plasma glucose (FPG).
CARDIAC			
Arterial hypertension	Dose modify/hold copanlisib because of association with arterial hypertension. May dose modify/hold ibrutinib as clinically indicated		
	Pre-dose measurements BP \geq 150/90 mmHg	Maintain ibrutinib dose per investigator discretion	Delay copanlisib until recovery to < 150/90 mmHg Consider BP lowering medication. Dosing can proceed on the scheduled day if after at least 2 consecutive measurements BP returns to < 150/90 mmHg. If BP doesn't return to < 150/90 mmHg, delay dosing until next visit.
	During infusion: Grade 3 (\geq 160/100 mmHg)	Dose adjustments of ibrutinib per investigator discretion	Infusion can be interrupted or slowed down and administration of BP lowering therapy should be initiated. Infusion maybe resumed when BP has returned to < 150/90 mmHg at the investigator's discretion or skipped. Subsequent study drug administrations maybe reduced by 1 dose level at the investigator's discretion.
